Using the UCSDHS EHR, we will conduct a query for a list of all potential participants who meet the eligibility criteria. We will use both Epic and Care Everywhere platforms to ascertain eligibility criteria for recruitment. Among the list of adults deemed eligible for recruitment, we will stratify individuals based on their EHR-documented race/ethnicity into one of five groups: Non-Hispanic White, Black, Hispanic, Asian/Pacific Islander, Other. From these groups, we will select a list of 20 individuals to be recruited. In sum, the 100 individuals will be comprised of 20 individuals selected at random from 5 self-reported racial/ethnic groups, with the intent that each racial/ethnic group will have 10 individuals represented in the mailed Cologuard outreach and mailed FIT outreach (each group makes up 20% of the sample in each arm). This will ensure equal balance of participants from each racial/ethnic group in each trial arm.

Eligible individuals will be mailed a postcard briefly describing the study and asking patients to scan a QR code if they are interested in participating. The QR code will take eligible individuals to eConsent forms within REDCap, where they will be provided with informed consent and HIPAA Authorization forms that will need to be completed to participate in the study. Electronically completed and signed informed consent and HIPAA authorization forms will be required prior to randomization. HIPAA Authorization is necessary to release relevant patient information to Exact Sciences, the company that will mail and implement the Cologuard test, should the participant be randomized to that group. Additionally, HIPAA Authorization ensures participant electronic health records may be examined to measure the study's outcomes of interest over the course of study follow-up.

If individuals decline participation or do not sign HIPAA authorization and informed consent documents, they will be replaced by another eligible individual from the same EHR-documented race/ethnicity grouping. After agreeing to participate, individuals within each race/ethnic group will

be assigned randomly to the mailed Cologuard outreach and mailed FIT outreach arms, such that an equal number of individuals from each group is included in each trial arm. Recruitment will continue until a sample size of 50 individuals per trial arm (mailed Cologuard outreach and mailed FIT outreach) who consent to participation in the study is achieved.

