It must be ensured that the individual understands every aspect of the study, including its risks and benefits, prior to signing the informed consent. Our study population of adults ages 45-49 receiving care at UCSDHS with a documented primary care provider are likely to have a low prevalence of documented cognitive capacity issues. Indications of potentially diminished cognitive capacity include: 1) diagnosis of dementia or cognitive impairment, 2) presenting for an evaluation of dementia or cognitive impairment, 3) a report, in medical records that the subject has symptoms of dementia or cognitive impairment, 4) psychotic symptoms, bizarre or abnormal behavior exhibited by the individual and 5) an abnormal degree of confusion, forgetfulness, or difficulties in communication that is observed in the course of interacting with the individual. To ensure our study participants have adequate decision-making capacity to participate, we will initially review potential participants' electronic health records for documented conditions or circumstances that are associated with possible decrease in decision-making capacity. If at the time of consent or during the study period of the pilot trial there is an indication that the participant's cognitive capacity is compromised, we will complete the University of California Office of the President [Decision-Making Capacity Assessment Tool](#) (hyperlink included) to measure the participant's cognitive capacity. If the participant is

determined to lack decision-making capacity at this point, their follow-up will be excluded from the study.

The consent of the individual to participate in the study and HIPAA research authorization will be recorded electronically on an eConsent form within REDCap. Copies of the signed and dated consent and HIPAA research authorization forms will be provided to the participant and placed in the participant's study file.

C. Risk and Benefits

Risks

Research risks include the following:

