intervention and usual care) who consent to participation in the study is achieved. Each group will be followed for 6 months for the primary outcome: completion of any CRC screening test (FIT, FIT-DNA [Cologuard], sigmoidoscopy, colonoscopy, or CT Colonography), measured by evidence of screening documented within the EHR using Healthcare Effectiveness Data and Information Set (HEDIS) criteria.

B. Blinding

Due to the nature of the interventions, the study team will not be blinded to group assignment. Patients will be notified prior to randomization of the existence of two study arms (mailed Cologuard outreach and mailed FIT outreach), and once randomized, will know whether they were assigned to Cologuard or mailed FIT outreach. From the date of randomization, participants will be followed for 3 months to ascertain the primary outcome: CRC screening completion, measured by evidence of screening documented within the EHR. Additional passive follow up through manual chart review will continue 9 months post randomization.

References

6. American Cancer Society. *Colorectal Cancer Facts & Figures 2020-2022*. American Cancer Society; 2020.

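### The capacity rule lets an unblinded team exclude a randomized participant's follow-up, even an outcome already in the health record, and no analysis set offsets it (minor)

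*Combined protocol and SAP*

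**What the plan says.** The rule is in Human Rights Issues and Informed Consent, B. Aim 2 Pilot Trial. It opens "If at the time of consent or during the study period of the pilot trial there is an indication" of compromised capacity. The study team then completes a named University of California capacity assessment tool, and if the participant is "determined to lack decision-making capacity at this point, their follow-up will be excluded from the study".

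The same section limits how often this should happen. The population is described as "likely to have a low prevalence of documented cognitive capacity issues", and potential participants are first checked by reviewing their "electronic health records for documented conditions or circumstances that are associated with possible decrease in decision-making capacity". Five indications are listed. Three rest on a diagnosis, an evaluation or a medical-record report. The other two are behavioural, and one of these includes "difficulties in communication that is observed in the course of interacting with the individual".

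Other sections fix the timing and the data source:

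- Patient Population, A. Recruitment and Screening Strategy (Aim 2): "Electronically completed and signed informed consent and HIPAA authorization forms will be required prior to randomization". It adds that "HIPAA Authorization ensures participant electronic health records may be examined" to measure the study outcomes.
- Study Outcome Measurements, A. Primary Endpoints (Aim 2): screening completion within 3 months of randomization is obtained by an EHR query.
- Stratification and Randomization, B. Blinding: "the study team will not be blinded to group assignment". Passive chart review continues to 9 months.

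**The concern.** Consent and authorization come before randomization, so a capacity finding during the study period will in general concern someone already randomized. Excluding that person's follow-up is a post-randomization exclusion, decided by people who know the arm and may be able to see the outcome. Randomization protects the comparison only if the people randomized are the people analysed.

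Obtaining the outcome does not require the exclusion. Completion is read from the EHR without contacting the participant, under an authorization signed earlier. Because follow-up runs to 9 months, a finding at month 6 could, on a literal reading, remove a 3-month outcome already on record.

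The documents define no intention-to-treat or other analysis set, no missing-data rule and no reporting of such exclusions. Replacement covers only people who decline or do not sign. One exclusion would therefore turn a planned 10:10 race/ethnicity stratum into 9:10 with no stated remedy. The pilot is meant to inform the power and sample size of a larger trial, so a loose rule could be carried forward.

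**Working it through.** **Does the rule reach randomized participants?**

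1. Signed consent and authorization precede randomization (Recruitment and Screening Strategy; Randomization).
2. The capacity rule covers consent and the study period. A finding at consent is before randomization and does no harm to the comparison. A finding in the study period generally comes after it.
3. The protocol says the study team completes the assessment, and Blinding says that team knows the arm.
4. No other section restores such a participant to the analysis.

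So the text permits post-randomization exclusion.

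**How much could it matter?** The plan gives no figure for such exclusions, so there is none to reproduce. The inputs come from Sample Size and Rationale: 50 per arm, FIT completion 23%, and a 15-point higher rate with Cologuard, hence 38%. Expected completers are 0.38 × 50 = 19 and 0.23 × 50 = 11.5. The planned difference is 38.0 − 23.0 = 15.0 points. (The 80% power stated there does not reproduce: a two-sided normal approximation gives 36.9%. That is a separate matter, and only the planning rates are used here.)

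Removing k people from an arm with x expected completers changes its rate from x/50 to x/(50 − k) if they are non-completers, or to (x − k)/(50 − k) if they are completers. The values k = 1, 2, 3 are assumptions. The difference in points becomes:

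| Removed | k = 1 | k = 2 | k = 3 |
|---|---|---|---|
| Cologuard non-completers | 19/49 − 0.23 = 15.8 | 19/48 − 0.23 = 16.6 | 19/47 − 0.23 = 17.4 |
| Cologuard completers | 18/49 − 0.23 = 13.7 | 17/48 − 0.23 = 12.4 | 16/47 − 0.23 = 11.0 |
| FIT non-completers | 0.38 − 11.5/49 = 14.5 | 0.38 − 11.5/48 = 14.0 | 0.38 − 11.5/47 = 13.5 |
| FIT completers | 0.38 − 10.5/49 = 16.6 | 0.38 − 9.5/48 = 18.2 | 0.38 − 8.5/47 = 19.9 |

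For a single exclusion the shift is p/49 for a non-completer and (1 − p)/49 for a completer:

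- FIT non-completer: 0.23/49 = 0.5 points, lowering the difference.
- Cologuard non-completer: 0.38/49 = 0.8 points, raising it.
- Cologuard completer: 0.62/49 = 1.3 points, lowering it.
- FIT completer: 0.77/49 = 1.6 points, raising it.

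**Compared with sampling error.** The 95% half-width on the difference is 1.96 × √(0.23 × 0.77/50 + 0.38 × 0.62/50) = 1.96 × 0.0909 = 17.8 points. One exclusion shifts the estimate by less than a tenth of that (1.6/17.8 = 0.09). With k = 0 nothing changes.

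**The case against.** The strongest case against is that this is a participant-protection clause and not an analysis rule. Its wording parallels the Aim 1 rule, which excludes interview responses, and it may mean only that later data collection stops. The consent section itself says that a signature alone is not informed consent. Consent here is remote, so incapacity found later may cast doubt on the original agreement. The expected count is near zero, in a feasibility pilot not sized for hypothesis testing.

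Most of this stands and sets the size of the point. It does not remove it: under the narrower reading, a randomized participant may still lack a primary outcome, with no stated handling. The ethical argument is why the remedy must depend on what the IRB permits.

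A reader might infer four stronger things that the documents do not support:

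- **That the trigger is purely subjective.** Three of the five indications are record-based, and none excludes anyone until the assessment tool has been completed.
- **That detection differs by arm because contact differs.** Cologuard support comes from the company's care centre, and nothing says it reports behaviour to the study team. FIT mailings involve no conversation.
- **That exclusion inflates completion.** Confused participants might be less likely to return a kit. But the study-team patient contact described in B. Secondary Endpoints arises when no correct primary care provider can be found to receive a result, so it concerns people who have already returned a test. Excluding one of them would lower completion.
- **That the comparison is broken.** The likely count and the shift per case are too small for that.

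**Conclusion.** The point holds as a minor one. Taken literally, the text allows an unblinded team to exclude follow-up after randomization, including a recorded primary outcome, and nothing else in the plan prevents it. The direction of any bias is unknown.

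The size rests on the planning rates and on assumed counts, since the documents give no frequency. Low expected prevalence and the prior EHR review make zero a plausible count. That the outcome remains available is supported by the EHR-based endpoint and the prior authorization. Whether it may still be used after a finding of incapacity is not settled in the documents and is for the IRB. The case for acting is that the source of bias is avoidable and cheap to close, not that it threatens the pilot.

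**What to change.** Leave the capacity assessment as it is and replace the sentence on its consequence with a rule split by timing:

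1. **Before randomization:** the person is not randomized.
2. **After randomization:** the participant stays in the primary analysis in the assigned arm, using EHR screening status, wherever the consent, HIPAA authorization and IRB permit. This includes any outcome recorded before the capacity finding.
3. **If the IRB does not permit use of the data:** exclude the participant from the primary analysis. Add a sensitivity analysis counting such participants as not completed only if the IRB allows it. That imputation should not be the primary analysis, because it could assign a false outcome.
4. **In all cases:** report the number, timing and reason of exclusions by arm.

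The cost is a few lines of protocol text and one IRB confirmation. No extra data collection is needed.

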This study employs a mixed methods design to develop a CRC screening strategy for adults ages 45-49. First, our study will employ interviews of pilot trial participants and providers involved in CRC screening referral and coordination to qualitatively examine factors influencing CRC screening uptake. In parallel, we will conduct a pilot randomized controlled trial to compare a mailed multi-target stool DNA test (Cologuard) outreach strategy to mailed fecal immunochemical test (FIT) outreach. Results from our interviews and the pilot trial will inform a larger, fully powered trial of Cologuard outreach vs. mailed FIT outreach for CRC screening.

A. Study Rationale

We chose to pursue this mixed methods design to simultaneously learn about factors at the patient, provider and system levels that might influence CRC screening uptake and examine the potential acceptability of a mailed Cologuard outreach strategy compared to mailed FIT outreach. The trial will enable us to conduct a real-world examination of potential uptake of CRC screening among adults ages 45-49, where evidence regarding CRC screening is currently limited.

We choose to test the mailed Cologuard outreach strategy as the primary pilot intervention because of its demonstrated efficacy among adults ages 50-75, and potentially greater acceptability as a screening modality compared to other available tests.³³ The control group will receive mailed FIT outreach, a strategy proven effective at increasing CRC screening uptake among individuals not up to date with screening.^{34,35} This control arm reflects a proven screening outreach strategy that has been implemented in many settings, including at University of California San Diego Health System.

We acknowledge that some adults ages 45-49 might be more inclined to utilize other screening modalities, such as colonoscopy. Thus, we are measuring screening uptake as an outcome of our study, to include any potential screening modality used as covered by the USPSTF guidelines. Our decision to consider any potential screening modality uptake as completed

screening is based on the ultimate goal of the study to maximize screening among this newly eligible screening population.

B. Study Population and Rationale

Aim 1. Interviews

The specific inclusion criteria for Aim 1 are:

Patient Participants

- Adults ages 45-49.
- EHR documentation indicating the patient has an assigned primary care provider at UCSDHS
- ≥1 UCSDHS health visit within the last year

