- 3) Patient results will be sent to the ordering provider within 2 weeks of test completion and return.

Patients with normal results will be sent a letter to repeat CRC screening in 3 years. Patients with abnormal results will be sent a letter encouraging follow up colonoscopy, and their primary care provider will be notified and requested to order colonoscopy. Patients with colonoscopy orders will receive usual care colonoscopy scheduling, preparation, and completion by the UCSDHS GI department. Notably, some clinicians at UCSDHS are already offering Cologuard as a usual care screening test.

2. Mailed fecal immunochemical test (FIT) outreach.

The control group to be tested in the pilot is mailed FIT outreach, a multi-component strategy found to have the largest effect size to improve CRC screening uptake compared to usual care.^{35,36} FIT is a USPSTF-recommended at-home screening test for blood in stool. Abnormal FIT results are followed up with a colonoscopy to identify and remove pre-cancerous polyps or diagnose early-stage CRC.³⁴ FIT test kits will be prepared at UCSD Health to be delivered to participants randomized to this study arm. Participants randomized to mailed FIT outreach will receive:

- 1) advanced notification (primer) via mail one week prior to receiving the FIT kit;
- 2) FIT kit normally offered at UCSDHS (Polymedco OC Light) with study information, invitation and instructions to complete FIT and how to opt-out; and
- 3) reminders via mail 14 days and 28 days after FIT kit receipt.

FIT kits will be mailed to UCSD Health System to undergo current usual care assay and reporting, based on the Polymedco OC Light criteria (the current test used within UCSDHS). Patients with normal results will be sent a letter to repeat CRC screening in a year. Patients with abnormal results will be sent a letter encouraging follow up colonoscopy, and their primary care provider will be notified and requested to order colonoscopy. Patients with colonoscopy orders will receive usual care colonoscopy scheduling, preparation, and completion by the UCSDHS GI department.

D. Outcome Measures and Rationale

1. Aim 1 Interview Constructs

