The primary study endpoint is colorectal cancer (CRC) screening completion within 3 months of randomization. We plan to measure this using Healthcare Effectiveness Data and Information Set (HEDIS) documentation to inform our CRC screening uptake variable. This variable will incorporate CPT, Healthcare Common Procedural Coding System (HCPCS), and ICD-9/10 coding to identify FIT or guaiac fecal occult blood tests (CPT: 82270, 82274; HCPCS: G0328), flexible sigmoidoscopy (CPT: 45330-45335, 45337-45342, 45345-45347, 45349, 45350; HCPCS: G0104; ICD-9: 45.24), colonoscopy (*CPT/HCPCS codes mentioned in **Table 1***; ICD-9: 45.22, 45.23, 45.25, 45.42, 45.43), CT colonography (CPT: 74261-74263) and FIT-DNA (Cologuard) tests (CPT: 81528, HCPCS: G0464). We will also conduct manual EHR review to validate our HEDIS-defined algorithm. After the initial EHR query to define our study population, we will do manual EHR review two times during the follow-up period, once in the first month after study start to test the HEDIS-defined algorithm and a follow-up review in the second month after study start to validate the final algorithm. At the end of 3 months of study follow-up we will use the validated final algorithm to query for CRC screening completion.

B. Secondary Endpoints

Aim 2 Pilot Trial Secondary Outcomes

In the pilot trial, we will measure multiple outcomes to assess feasibility of a larger trial. We will measure the total number of participants who opt out of the pilot as a recruitment outcome. We will also measure the number of participants with undeliverable Cologuard or FIT kits, known as mail fail rate, as an intervention outcome. Among those with abnormal Cologuard or FIT, we will measure the proportion who are referred to colonoscopy and proportion who complete colonoscopy. We will measure the proportion who are referred to colonoscopy and the proportion who complete colonoscopy via manual EHR review of participants with abnormal Cologuard or

FIT results. We will conduct the manual EHR review 3 months, 6 months and 9 months after randomization, only among randomized study participants (those who provided signed HIPAA authorization and informed consent).

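### Care Everywhere is named for eligibility but not for the any-modality primary outcome, so screening with a non-study test outside UCSDHS may be counted as not completed

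*Combined protocol and SAP*

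**What the plan says.** **Eligibility.** Patient Population, A. Recruitment and Screening Strategy (Aim 2) and Stratification and Randomization, A. Randomization both begin with a query of the UCSDHS EHR and then state: "We will use both Epic and Care Everywhere platforms to ascertain eligibility criteria for recruitment". Exclusion Criteria Data Ascertainment adds a check of problem lists and other EHR sources, and gives the health maintenance registry as an example.

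**Primary outcome.** Study Rationale wants uptake measured broadly, "to include any potential screening modality used as covered by the USPSTF guidelines", because some participants may prefer a test such as colonoscopy. Study Outcome Measurements, A. Primary Endpoints (Aim 2) defines the variable under HEDIS: "This variable will incorporate CPT, Healthcare Common Procedural Coding System (HCPCS), and ICD-9/10 coding". It is scored as follows: "At the end of 3 months of study follow-up we will use the validated final algorithm to query for CRC screening completion". Stratification and Randomization, B. Blinding describes the same outcome as "CRC screening completion, measured by evidence of screening documented within the EHR".

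**Manual review.** For the primary outcome, "We will also conduct manual EHR review to validate our HEDIS-defined algorithm". Primary Endpoints places this review in the first and second months after study start. Reviews at 3, 6 and 9 months are described for colonoscopy follow-up of abnormal kits. Blinding also mentions passive chart review to 9 months and does not say what it is for.

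**Study kits.** Intervention Regimens and Rationale says of FIT: "FIT kits will be mailed to UCSD Health System to undergo current usual care assay and reporting". Of Cologuard it says: "Patient results will be sent to the ordering provider within 2 weeks of test completion and return".

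**Not stated.** No section names Care Everywhere, claims or participant report as an outcome source. None says how a participant is classified who is screened elsewhere or leaves UCSDHS.

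**The concern.** An outside colonoscopy found in Care Everywhere makes a person ineligible before randomization. After randomization, nothing in the plan says that the same record would be looked for. Yet the outcome deliberately counts tests that the study did not supply, and those are the tests most likely to be done somewhere else.

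The documents themselves expect some loose attachment to the system. Eligibility requires an assigned primary care provider and one visit in the past year. Secondary Endpoints plans for wrong provider assignments, and Protection Against Risk foresees participants becoming uninsured.

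At stake is misclassification of the primary outcome in a pilot whose Aim 2 hypothesis says that it will inform the final power and sample size of the larger trial. If completers are missed, the arm-level rates carried forward are too low. If they are missed unequally, the difference between arms is wrong as well.

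**Working it through.** **Step 1. Sources set side by side.**

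| Source | Named for eligibility | Named for the primary outcome |
|---|---|---|
| UCSDHS EHR, coded data | Yes | Yes |
| Health maintenance registry | Yes, as an EHR source | Not by name |
| Care Everywhere | Yes | No |
| Manual review | Not described as the method | To test and validate the code algorithm, not to score each participant at 3 months |

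**Step 2. Who is exposed.**

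- FIT kit returned: assayed at UCSD Health, so the result is in the system even if the participant has since changed provider or insurer.
- Cologuard kit returned: the result goes to the study's ordering provider. The documents do not say how that result becomes a code in the EHR, but it does reach the study.
- Non-study test at UCSDHS: coded in the EHR.
- Non-study test outside UCSDHS within the outcome window: visible only if the query reaches outside records. This is the exposed group.

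**Step 3. Size.** The inputs from Sample Size and Rationale are 50 per arm, 23% completion assumed with mailed FIT, and a difference of 15 points, which implies 38% with Cologuard. The documents give no rate of outside screening. Let m be the share of an arm's completers that the query misses. Values of 5% and 10% are assumed here for illustration.

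- One missed completer: 1/50 = 2 percentage points in that arm.
- Expected completers: 0.23 × 50 = 11.5 with FIT and 0.38 × 50 = 19 with Cologuard. A loss of 5-10% is about 0.6-1.2 and 1.0-1.9 people.
- Observed rate = true rate × (1 − m):

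| Assumed loss | FIT | Cologuard | Difference (points) |
|---|---|---|---|
| None | 23.0% | 38.0% | 15.0 |
| 5% in both arms | 21.85% | 36.1% | 14.25 (14.3) |
| 10% in both arms | 20.7% | 34.2% | 13.5 |
| 5% in Cologuard only | 23.0% | 36.1% | 13.1 |
| 10% in Cologuard only | 23.0% | 34.2% | 11.2 |
| 5% in FIT only | 21.85% | 38.0% | 16.15 (16.2) |
| 10% in FIT only | 20.7% | 38.0% | 17.3 |

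The one-arm rows show that the sign of the error depends on which arm loses more, and the documents do not settle that.

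**The plan's own figure.** The section states 80% power for this difference. That figure is not used here and does not reproduce: 23% against 38% with 50 per arm, two-sided at 0.05, gives 36.9% by the normal approximation with pooled null variance. That is a separate matter, and the present point does not rest on it.

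**The case against.** The strongest reply is that the plan leaves a detail open and does not state a bad rule. The Randomization section introduces eligibility as a query of the UCSDHS EHR and in the next sentence names Epic and Care Everywhere as the platforms. On that usage, the EHR in the outcome definition could include Care Everywhere. The registry is explicitly called an EHR source. The passive chart review to 9 months is not limited to abnormal kits where Blinding mentions it. Participants must also be insured, live locally, have an assigned UCSDHS provider and have been seen within the year, which narrows the chance of outside screening within 3 months. The pilot is not sized for hypothesis testing.

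Much of this stands. A reader might infer that everyone screened elsewhere, and everyone who leaves UCSDHS, is scored as not screened. The documents do not support that. They state no such classification rule, they do not exclude Care Everywhere from the EHR, and a participant who leaves but returns the study kit still produces a result that reaches the study.

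The reply does not close the gap. The stated scoring method at 3 months is a code query. The manual reviews whose purpose is given either validate that query or follow abnormal kits. The scope of the passive review is unclear. Care Everywhere is named each time eligibility is ascertained and never for the outcome.

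**Conclusion.** The point holds in a limited form. As written, the plan ascertains eligibility from a wider set of named sources than the primary outcome. Screening with a non-study test outside UCSDHS may therefore be counted as not completed. Study kits are largely protected.

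The only firm figure is 2 percentage points per missed completer in an arm of 50. The fall from 15 points to 14.3-13.5 rests on an assumed equal loss of 5-10% of completers. That is probably a generous base, since the exposure lies mainly among people who did not use the kit. It would be going too far to say that completion is understated as a matter of fact, or that one arm is favored: neither the rate of outside screening nor its balance between arms can be had from the documents.

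The change is still worth making. It replaces a stated method with a better one at low cost, in a pilot whose rates are meant to feed the next trial's sample size.

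**What to change.** In Study Outcome Measurements, A. Primary Endpoints, and in Stratification and Randomization, A and B:

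- Ascertain the primary outcome for all randomized participants from the sources used for eligibility: Epic codes, the health maintenance registry and Care Everywhere.
- Count a test by its documented date within the primary window, with identical objective criteria in both arms.
- Report by arm the number of participants with evidence of having left UCSDHS.
- Reconcile the window. Primary Endpoints and Blinding say 3 months, while the end of the Randomization section says 6 months. A longer window leaves more time for outside screening or departure.
- Confirm that the signed HIPAA authorization covers outside records. The plan describes it as covering participants' electronic health records and names no outside source.

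The cost is a modest chart look-up for 100 consented participants. Blinding says that the study team knows the assignments, so the look-up adds some room for judgment. Requiring a documented test and date, and searching every participant in the same way, limits that.
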